12.5.2 Safety endpoints

For all safety analyses, the safety set will be used. All subjects enrolled into the extension study, regardless of which preceding studies they came from will be included in the safety analysis. All listings and tables will be presented by treatment group. All data will be included in the analysis regardless of rescue medication use.

Adverse events (AEs)

[figure not shown]
Treatment emergent AEs will be summarized by treatment group. Treatment emergent AEs are defined as the events started after the first dose of study treatment within 16 weeks of last dose of study treatment, or events present prior to the first dose of study treatment but increased in severity based on preferred term within 16 weeks after the last dose of the study treatment.

The number (and percentage) of subjects with treatment emergent AEs will be summarized in the following ways:

- by treatment, primary system organ class and preferred term.
- by treatment, primary system organ class, preferred term and maximum severity.

Separate summaries will be provided for study medication related AEs, death, SAEs, other significant AEs leading to discontinuation. The number (and proportion) of subjects with AEs of special interest/related to identified and potential risks will be summarized by treatment. A subject with multiple AEs within a primary system organ class is only counted once towards the total of the primary system organ class.

AEs which will be counted for a specific treatment period are those which are treatment-emergent. These events are those with an onset after the start of the treatment period, or which

were present prior to the start of the treatment period but increased in severity, and developed into SAEs after the start of the treatment period.

For safety and tolerability of ligelizumab for all subjects during the study, a summary table will be provided for the two subgroups of subjects below:

- Subjects who receive two years continuous ligelizumab treatment.
- Subjects who receive one year ligelizumab treatment and move to the second observation period before move to the second half of the treatment.

To investigate the safety and tolerability of ligelizumab 120 mg PFS, a summary table will be provided to include the AEs after the first dose of PFS use. Only the subjects who receive at least one dose of ligelizumab 120 mg PFS use will be included in this analysis.

To investigate the safety and tolerability of ligelizumab 120 mg in all subjects who will be self-administered, a summary table will be provided to include the information after the first dose using self-administration. Subjects who move from self-administration back to in-clinic administration during the study, they will be included in this analysis if majority (>50%) of drug use is based on self-administration.

SAE summaries will be provided in a similar manner.

Vital signs

Analysis of the vital sign measurements using summary statistics for the change from baseline for each post-baseline visit will be performed. These descriptive summaries will be presented by vital sign and treatment group. Change from baseline will only be summarized for subjects with both baseline and post-baseline values. Subjects with notable vital signs as defined in [Appendix 1](#) will be listed.

12-lead electrocardiogram (ECG)

All ECG data will be listed by treatment group, subject and visit/time, abnormalities will be flagged. Summary statistics will be provided by treatment and visit/time.

Clinical laboratory evaluations

The summary of laboratory evaluations will be presented for 2 groups of laboratory tests (hematology and serum chemistry). Descriptive summary statistics for the change from baseline to each study visit will be presented. These descriptive summaries will be presented by laboratory test and treatment group. Change from baseline will only be summarized for subjects with both baseline and post baseline values. Shift tables using the low/normal/high/ (low and high) classification will be used to compare baseline to the worst on-treatment value.

Other safety evaluations

[REDACTED]

[REDACTED]

[figure not shown]
[REDACTED]

[figure not shown]
Resource utilization

Data relating to resource utilization will be used for the purpose of economic evaluation and will be carried out and reported as a separate activity.

[figure not shown]

[figure not shown]
12.5.5 Biomarkers

Available biomarker data will be listed by treatment group, subject and visit. Summary statistics will be provided by treatment and visit. The number of values outside of the limits of quantification will be reported in each table.

12.7 Interim analyses

The first interim analysis is planned once all subjects of the CQGE031C2302 and CQGE031C2303 have completed Week 12 (Visit 204) in the first half of the treatment period to evaluate the primary endpoint of retreatment efficacy (or discontinued the trial or completed the first observation period without relapse).

The second interim analysis will be performed at the end of the first half of the treatment period at Week 52 to evaluate endpoints up to the end of 1 year treatment.

Additional analyses may be performed to support health authority interactions as necessary.

[figure not shown]
At the End of Study, a final analysis of all data collected up to last study visit will be performed when all subjects have completed the last study visit.

12.8 Sample size calculation

12.8.1 Primary endpoint(s)

The total number of subjects enrolled will be determined by the drop-out rate prior to the Phase 3 extension study from studies CQGE031C2302, CQGE031C2303, CQGE031C2202 and CQGE031C1301.

Based on interim results from CQGE031C2201, it is assumed that the proportion of subjects achieving $UAS7 \leq 6$ at Week 12 is around 55% for ligelizumab 72 mg q4w. It is assumed that the well-controlled response for ligelizumab 120 mg q4w will be similar. The corresponding

95% confidence interval is listed based on different assumptions of number of subjects who will be enrolled for each treatment arm.

Table 12-1 95% confidence interval based on number of subjects enrolled from the core studies (CQGE031C2302/2303)

Number of subjects enrolled	Number of subjects for each treatment group	Drop out rate at Week 12	Assumed proportion of subjects achieving UAS7 ≤ 6 at Week 12	Corresponding 95% confidence interval
500	250	10%	55%	(48.6% - 61.6%)
900	450	10%	55%	(50.2% - 59.9%)
1200	600	10%	55%	(50.8% - 59.2%)

To evaluate the retreatment efficacy in the subgroup of subjects who achieved $UAS7 \leq 6$ at Week 12 after the retreatment on the same ligelizumab dose, the 95% confidence interval of the response rate will be provided for each treatment group. It is assumed that 50% of subjects enrolled into this extension study were well-controlled responders during the core studies for each ligelizumab treatment group. A 15% drop out rate is assumed for each treatment group before Week 12. The number of subjects required at the baseline of re-treatment for each treatment arm is listed in [Table 12-2](#) below, based on different assumptions of the retreatment response rates and the corresponding precision levels (width of the 95% confidence interval).

Table 12-2 Number of subjects required at the baseline of re-treatment for each treatment arm enrolled from the core studies (CQGE031C2302/2303)

Response rate after retreatment	Precision		
	10%	12%	15%
70%	191	135	85
80%	146	102	66
90%	83	59	38

[figure not shown]
13 Ethical considerations and administrative procedures

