4.1 Rationale for study design

Data from the dose-range finding Study CQGE031C2201 demonstrated that ligelizumab treatment improves itch and hives in adult subjects with CSU who have failed treatment with H1-antihistamines and those who failed treatment with a combination of H1- and H2-antihistamines and a LTRA. [REDACTED]

This Phase 3 extension study is designed to build on [REDACTED] previous and ongoing study data by further evaluating longer-term safety and efficacy, keeping in mind that many patients with CSU will have their disease for many years, and there is currently a knowledge gap in long-term management of CSU with ligelizumab.

The target population for this study consists of all CSU adult and adolescent subjects who have completed studies CQGE031C2302, CQE031C2303, CQGE031C2202 or CQGE031C1301. In these ongoing Phase 3 and CQGE031C2202 adolescent studies, the population consists of patients who remain symptomatic despite treatment with H1-AHs at locally approved doses. In the CQGE031C2302 and CQE031C2303 studies, subjects were randomized (3:3:3:1) to receive ligelizumab 72 or 120 mg q4w or omalizumab 300 mg q4w for 52 weeks treatment period or placebo for 24 weeks then ligelizumab 120 mg q4w for the rest of the 52 week treatment period. In the CQGE031C2202 adolescent study, subjects are randomized (1:2:1) to receive ligelizumab 120 mg q4w for 24 weeks, ligelizumab 24 mg q4w for 24 weeks or placebo for 12 weeks followed by 120 mg q4w for the following 12 weeks. In the CQGE031C1301 open label Japan safety study, subjects receive ligelizumab 120 mg q4w for the 52 weeks treatment period.

Subjects from the core studies (CQGE031C2302 and CQGE031C2303) and the CQGE031C2202 adolescent study will not be unblinded in order to enter this extension study.

This study will remain blinded until all subjects who have transitioned from the Phase 3 core studies have completed Visit 204 (Week 12) in this study, and the primary analysis has been completed after which it will be open-label. Such a study design was chosen to maintain the blind in the Phase 3 core studies and to avoid any bias in primary efficacy assessments due to knowing the dose the subjects received in the Phase 3 core studies.

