12.4.2 Statistical model, hypothesis, and method of analysis

To show retreatment efficacy of ligelizumab 120 mg q4w or 72 mg q4w in achieving well-controlled CSU at Week 12 in the first half of the treatment period in subjects transitioning from the core studies, the summary statistics for the proportion of subjects achieving $UAS7 \leq 6$ at Week 12 of the first half of the treatment period in this extension study will be provided. The primary analysis will be performed for subjects receiving the same dose of ligelizumab they received in the core studies, i.e. 72 mg or 120 mg for one year. The corresponding 95% confidence interval also will be derived based on the score method including continuity correction.

For the subgroup of subjects who achieved $UAS7 \leq 6$ at Week 12 in the core studies, and who received either 72 mg or 120 mg ligelizumab, the proportion of subjects with the response of $UAS7 \leq 6$ at Week 12 of the first half of the treatment period in this extension study will be provided together with a 95% confidence interval.

Subjects rolling over from study CQGE031C1301, who received ligelizumab 120 mg, will not be included in this primary analysis. As this is an open-label Japan safety study, the efficacy data for these subjects will be analyzed separately to avoid potential confounding issues.

Subjects rolling over from the adolescent PK/PD study CQGE031C2202 will also not be included in this primary analysis, as they received treatment doses of ligelizumab of 24 mg or 120 mg for different treatment times. The efficacy data for these subjects will be analyzed separately.

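### Protocol Table 12-2 and SAP Table 3-2 label half-widths as the width of the 95% confidence interval; the true widths are about 20, 24 and 30 points, not 10, 12 and 15

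*Protocol*

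**What the plan says.** The second primary objective (protocol Table 2-1, SAP Table 1-1) is retreatment efficacy in subjects who reached UAS7 ≤ 6 at Week 12 of the core studies. Protocol 12.8.1 plans it by precision and promises that "the 95% confidence interval of the response rate will be provided for each treatment group". Two planning inputs follow: "It is assumed that 50% of subjects enrolled into this extension study were well-controlled responders during the core studies" and "A 15% drop out rate is assumed for each treatment group before Week 12". Table 12-2 then gives the number per arm at the baseline of re-treatment for response rates of 70%, 80% and 90%, against "the corresponding precision levels (width of the 95% confidence interval") of 10%, 12% and 15%.

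SAP 3.1 repeats the text and all nine numbers in Table 3-2. Neither document uses the term half-width or a plus/minus sign for these columns.

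The tables do not fix recruitment: "The total number of subjects enrolled will be determined by the drop-out rate prior to the Phase 3 extension study". For the primary proportion, protocol 12.4.2 says "The corresponding 95% confidence interval also will be derived based on the score method including continuity correction". It names no method for the responder-subgroup interval.

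**The concern.** The labelled widths are too narrow for the numbers beside them, and Section 12.8.1 shows this without outside information. In Table 12-1, 250 per group less 10% drop-out leaves 225 evaluable, and the stated interval of 48.6% to 61.6% is 13 points wide. In Table 12-2, 191 per arm leaves about 81 evaluable responders (191 × 0.50 × 0.85), yet the label promises a width of 10 points at a 70% response. Moving from 55% to 70% narrows an interval by only about 8%, since √(0.21/0.2475) = 0.92. So 81 subjects cannot give a narrower interval than 225.

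The study is estimation only (SAP 2.5.2), so precision is the whole sample-size justification, and Table 12-2 is the only such statement for this objective. As labelled, Table 12-1's smallest group of 250 would give a 10-point-wide interval at all three response rates, because 250 exceeds 191, 146 and 83. It does so at none of them.

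**Working it through.** **Inputs** (protocol 12.8.1): two-sided 95% interval, z = 1.96; response p = 70%, 80%, 90%; responder share 0.50; retention 1 − 0.15 = 0.85. The fraction of an arm that contributes is 0.50 × 0.85 = 0.425.

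**Formula.** Evaluable responders for half-width h: n = 1.96² p(1 − p)/h², rounded up. Subjects per arm: N = n/0.425, rounded up.

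**Step 1: reproduce the table, taking 10/12/15% as half-widths.** For p = 70% and h = 10%: 3.8416 × 0.21/0.01 = 80.67, so n = 81; 81/0.425 = 190.6, so N = 191, as listed.

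| Response | n for h = 10/12/15% | N computed | N listed |
|---|---|---|---|
| 70% | 81/57/36 | 191/135/85 | 191/135/85 |
| 80% | 62/43/28 | 146/102/66 | 146/102/66 |
| 90% | 35/25/16 | 83/59/38 | 83/59/38 |

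All nine cells match.

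**Step 2: take 10/12/15% as full widths, as the text says** (h = 5/6/7.5%). For p = 70% and a 10-point width: 3.8416 × 0.21/0.0025 = 322.7, so n = 323 and N = 760.

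| Response | n | N needed | N listed |
|---|---|---|---|
| 70% | 323/225/144 | 760/530/339 | 191/135/85 |
| 80% | 246/171/110 | 579/403/259 | 146/102/66 |
| 90% | 139/97/62 | 328/229/146 | 83/59/38 |

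No cell matches. Full-width variants also fail: dropping the responder inflation, dropping all inflation, a one-sided z, or inflating by 1.15 × 2. The continuity-corrected score interval matches no cell, either as a full width or as a half-width.

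**Step 3: actual full widths at the listed N** (evaluable n = 0.425 N; Wald width = 2 × 1.96 √(p(1 − p)/n)), in percentage points.

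| Response | Wald, columns 10/12/15% | Score with continuity correction |
|---|---|---|
| 70% | 19.9/23.7/29.9 | 20.7/24.7/31.2 |
| 80% | 19.9/23.8/29.6 | 21.1/25.4/31.8 |
| 90% | 19.8/23.5/29.3 | 22.9/27.7/35.3 |

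**Step 4: responder widths at Table 12-1's group sizes** (Wald, same 0.425; 250/450/600 per group).

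| Response | Full width (points) |
|---|---|
| 70% | 17.4/13.0/11.2 |
| 80% | 15.2/11.3/9.8 |
| 90% | 11.4/8.5/7.4 |

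**Step 5: check on Table 12-1 itself.** With 124/225, 223/405 and 297/540 responders, Wald gives 48.6–61.6, 50.2–59.9 and 50.8–59.2, as stated. The continuity-corrected score method gives 48.4–61.7, 50.1–60.0 and 50.7–59.2. No limit moves by more than 0.3 points, so those intervals are not in question.

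**The case against.** The case for leaving this alone is that it is one wrong word over correct arithmetic. The column heading says only *Precision*, which many readers take as a margin of error. Nothing depends on the table: enrolment follows roll-over and no inference is planned. The study was also terminated after the April 2022 decision (end of SAP Section 1), so reported intervals will come from actual counts. All of this stands, and it limits the weight of the point. It does not remove it, because the parenthesis explicitly defines precision as the width, and the definition was carried unchanged into SAP Amendment 3.

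A second objection is that 0.425 N removes drop-outs, whereas the planned analysis keeps most of them, through retrieved data or non-responder imputation (protocol 12.4.3). That is fair. The factor mirrors the sponsor's own planning input. With all responders retained (0.50 N), the 70% row becomes about 18.4/21.9/27.6 points, still nearly twice the label. Even counting every listed subject as an evaluable responder, against the text, the widths are about 13/15/19 points.

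A third point concerns Table 12-1, whose first column does not say whether it counts all core roll-overs or only those from the two same-dose arms. Core randomisation was 3:3:3:1, so the 50:50 split fits only the second meaning. That is also the natural reading given the lead-in, "based on different assumptions of number of subjects who will be enrolled for each treatment arm", and on it the intervals are correct. This is a request for a definition, not an error.

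**Conclusion.** The concern holds. Protocol 12.8.1 and SAP 3.1 state the precision for a primary objective as twice as good as the listed numbers deliver. The intervals are about 20, 24 and 30 points wide by the Wald formula that generated the table, and 20.7 to 35.3 points by the continuity-corrected score method. The identification of half-widths rests on the documents' own 50% and 15% and on nine exact matches. The widths assume those two inputs hold. The consequence is confined to the stated planning precision: the trial is not shown to be undersized and no analysis changes. It should be corrected because it is a demonstrable twofold misstatement that costs little to put right.

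**What to change.** In protocol 12.8.1 and SAP 3.1, replace *width* with *half-width* and head the columns of Tables 12-2 and 3-2 ±10%, ±12% and ±15%. The nine numbers stay as they are. Only if full widths were intended should they be replaced, by 760/530/339, 579/403/259 and 328/229/146 (Wald, same rounding).

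In the same edit, say that the table uses the normal approximation and name the interval method for the responder subgroup. It would also help to define the first column of Table 12-1 / 3-1 as roll-overs from the two same-dose ligelizumab arms, if that is what is meant; its intervals then stand.

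The cost is wording and column labels in one section of each document, with no extra patients and no change to any analysis. A protocol change formally needs an amendment under protocol 14.1. With the study terminated, correcting the SAP and stating the half-width meaning in the study report would serve the reader equally well.

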13.1 Regulatory and ethical compliance

This clinical study was designed and shall be implemented, executed and reported in accordance with the International Council for Harmonisation (ICH) Harmonized Tripartite Guidelines for Good Clinical Practice, with applicable local regulations (including European Directive 2001/20/EC, US CFR 21), and with the ethical principles laid down in the Declaration of Helsinki.

13.2 Responsibilities of the investigator and IRB/IEC

Before initiating a trial, the investigator/institution must obtain approval/favorable opinion from the IRB/IEC for the trial protocol, written ICF, consent form updates, subject recruitment procedures (e.g. advertisements) and any other written information to be provided to subjects. Prior to study start, the investigator is required to sign a protocol signature page confirming

his/her agreement to conduct the study in accordance with these documents and all of the instructions and procedures found in this protocol and to give access to all relevant data and records to Novartis monitors, auditors, Novartis Quality Assurance representatives, designated agents of Novartis, IRBs/IECs, and regulatory authorities as required. If an inspection of the clinical site is requested by a regulatory authority, the investigator must inform Novartis immediately that this request has been made.

13.3 Publication of study protocol and results

The protocol will be registered in a publicly accessible database such as clinicaltrials.gov and as required in European Union Drug Regulating Authorities Clinical Trials Database (EudraCT). In addition, after study completion (defined as last patient last visit) and finalization of the study report the results of this trial will be submitted for publication and posted in a publicly accessible database of clinical trial results, such as the Novartis clinical trial results website and all required Health Authority websites (e.g. Clinicaltrials.gov, EudraCT etc.).

For details on the Novartis publication policy including authorship criteria, please refer to the Novartis publication policy training materials that were provided at the trial investigator meetings.

13.4 Quality Control and Quality Assurance

Novartis maintains a robust Quality Management System that includes all activities involved in quality assurance and quality control, to ensure compliance with written Standard Operating Procedures as well as applicable global/local GCP regulations and ICH Guidelines.

Audits of investigator sites, vendors, and Novartis systems are performed by auditors, independent from those involved in conducting, monitoring or performing quality control of the clinical trial. The clinical audit process uses a knowledge/risk based approach.

Audits are conducted to assess GCP compliance with global and local regulatory requirements, protocols and internal SOPs, and are performed according to written Novartis processes.

13.5 Patient Engagement

The following patient engagement initiatives are included in this study and will be provided as available, for distribution to study participants at the time points indicated. If compliance is impacted by cultural norms or local laws and regulations, sites may discuss modifications to these requirements with Novartis.

- Thank You letter – end of trial
- Plain language trial summary – after Clinical Study Report publication

14 Protocol adherence

This protocol defines the study objectives, the study procedures and the data to be collected on study participants. Additional assessments required to ensure safety of subjects should be administered as deemed necessary on a case by case basis. Under no circumstances including incidental collection is an investigator allowed to collect additional data or conduct any additional procedures for any purpose involving any investigational drugs under the protocol,

other than the purpose of the study. If despite this interdiction prohibition, data, information, observation would be incidentally collected, the investigator shall immediately disclose it to Novartis and not use it for any purpose other than the study, except for the appropriate monitoring on study participants.

[figure not shown]
Investigators ascertain they will apply due diligence to avoid protocol deviations. If an investigator feels a protocol deviation would improve the conduct of the study this must be considered a protocol amendment, and unless such an amendment is agreed upon by Novartis and approved by the IRB/IEC and Health Authorities, where required, it cannot be implemented.

